5.3.2 Restrictions

Subjects will be administered the drug products in sitting posture. Subjects will avoid severe physical exertion during sampling hours.

Methylxanthine-containing food or beverages and grapefruit, orange, cranberry or juices of these three fruits are not allowed for 24 hours before and during the entire sampling days. Consumption of alcohol-based products is restricted for 24 hours before and during the entire sampling days.

Any concomitant medications (including non-prescription medication, multi-vitamin preparations or herbal medications) are prohibited during the whole study (from Screening Visit to the Follow-Up Visit).

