5.3.3 Criteria for Subjects' Withdrawal from the Study

The Investigator may withdraw a subject from the study based on following reasons:

1. Withdrawal of subject's consent;
2. Significant protocol violation, such as non-compliance with restriction regarding alcohol and drug use, and non-adherence to the the fasting condition;
3. Adverse events, as assessed by the Investigator to affect the subject safety or the outcome of the study endpoints;
4. Difficulties with blood collection;
5. Subject who vomits anytime during PK blood sampling periods will be excluded from the remainder of the study (including the rest of the periods if the adverse event occurred in the earlier ones). The subject will be advised to remain in the clinic for the rest of the confinement period for observation and so any safety related study procedures can be carried out;
6. Subject reports adverse events of diarrhea (more than three episodes of loose stools) in any PK blood sampling period, which could render the plasma concentration-time profile unreliable;
7. Subject is uncooperative during the study;
8. Use of any ongoing or concomitant medication.

Subject may withdraw from the study at any time without any reason. Subjects who do not attend Study Check-In or withdraw during the study will be recorded in the Log Book of Non-Conformities Work. If the subject discontinues from the study at any time after taking

the first dose of the study drug, the CRF would be completed accordingly and drug concentration will be analyzed. If a subject is discontinued early, all termination evaluations will be performed at the time of discontinuation. Details of reasons for premature withdrawal of subjects will be documented in the final study report.

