11.2 Statistical Analysis

Safety data will be evaluated for all subjects who received at least one dose of study medication. The data from subject(s) who received concomitant medication(s) or experienced diarrhea or vomiting during PK blood sampling periods, which could render the plasma concentration-time profile unreliable as stated on section 5.3.3, may be excluded

for that period from the pharmacokinetic analysis and statistical evaluation. The decision to exclude is made before bioanalysis.

Statistical analyses will include data from all subjects who have valid primary endpoints available for both periods of the study. The plasma concentrations obtained from the bioanalytical laboratory for subjects who have been withdrawn from the study due to adverse events or as list on section 5.3.3 will not be used for statistical evaluation.

The statistical method for testing bioequivalence is ANOVA for two-period, two-sequence, two-treatment cross-over comparing AUC_{0-t} and C_{max} after logarithmic (ln) transformation of the original values. The terms to be used in the ANOVA model are sequence, subject within sequence, period, and formulation.

Bioequivalence is concluded if the 90% confidence interval of the Test/Reference geometric means ratio is in the range of 80.00-125.00%, for AUC_{0-t} and C_{max} . This acceptance criterion is according to the Guideline on the Investigation of Bioequivalence, EMA, London, 2010; ASEAN Guideline for the Conduct of Bioequivalence Study, Lao PDR, 2015; and *Indonesian guidelines, Pedoman Uji Bioekivalensi, Badan Pengawas Obat dan Makanan (BPOM), Jakarta, 2015, page 37-38.*

Non-compartmental standard methods computation of PK parameters will be performed. Details will be provided in the final study report. Phoenix® WinNonlin (Version 8.0 or higher) (PPD [REDACTED]) will be used to perform the statistical analyses of AUC_{0-t} and C_{max} using analysis of variance (ANOVA) after transformation of the data to their natural logarithmic (ln) values. Mean treatment differences will be estimated using the ANOVA model above. 90% confidence intervals will be computed for the treatment differences based on the residual error term. Differences and CIs will result in ratios and corresponding CIs after back-transformation.

The difference in t_{max} will be analyzed non-parametrically on the original data using Wilcoxon matched-pairs test.

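### Does the permissive wording in Protocol 11.2 on diarrhoea, vomiting and concomitant medication leave the bioequivalence analysis set open?

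*Protocol*

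**What the plan says.** Protocol 11.2 makes two statements about these data. Data from a period with concomitant medication, diarrhoea or vomiting, "which could render the plasma concentration-time profile unreliable as stated on section 5.3.3, may be excluded"; on timing, "The decision to exclude is made before bioanalysis". The next paragraph is firm: concentrations of subjects "withdrawn from the study due to adverse events or as list on section 5.3.3 will not be used for statistical evaluation".

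The firm rule depends on withdrawal, and Protocol 5.3.3 opens with "The Investigator may withdraw a subject from the study based on following reasons". The listed reasons include:

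- no. 5: "Subject who vomits anytime during PK blood sampling periods will be excluded from the remainder of the study"
- no. 6: "Subject reports adverse events of diarrhea (more than three episodes of loose stools) in any PK blood sampling period"
- no. 8: "Use of any ongoing or concomitant medication"

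SAP 10.1 lists as *important* deviations both a subject who meets a withdrawal criterion but stays in, and a subject who takes an excluded medication. SAP 10.2 admits to the PK set only subjects with no *relevant* PK deviation, nothing likely to disturb comparability, and valid primary endpoints under both treatments. SAP 12.2.2 requires every reason for exclusion to be reported and refers to SAP 10.1.

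**The concern.** For diarrhoea and concomitant medication, both steps are optional as worded: the investigator may withdraw, and the data may be excluded. A subject with more than three loose stools in period 1 who is not withdrawn could complete period 2 and, on a literal reading, be counted or not. The SAP says *important* in one section and *relevant* in the next and does not define the second term. For vomiting, 5.3.3 no. 5 is firmer than 11.2.

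The medication trigger is also wide. Sections 5.3.2 and 5.3.3 no. 8 cover any medication, yet inclusion criterion 10 requires contraception and names oral and implanted methods.

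Protocol 6.2 leaves dosing staff and subjects unblinded, Protocol 2.4 lists vomiting and diarrhoea as common reactions, and nobody is named as the person who decides. At stake would be a primary analysis set chosen with knowledge of the product taken.

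**Working it through.** **1. The rules applied to each case**

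- *Above-threshold diarrhoea, subject withdrawn.* Out, by the second paragraph of 11.2.
- *Above-threshold diarrhoea, subject not withdrawn.* 5.3.3 no. 6 itself describes such a profile as possibly unreliable. SAP 10.1 makes the failure to withdraw an important deviation, and SAP 10.2 shuts out factors that disturb comparability. The natural reading is out.
- *Vomiting.* No. 5 ends participation, so a period 1 event leaves no second period. For a period 2 event, the second paragraph of 11.2 removes the withdrawn subject.
- *Concomitant medication.* Judgement remains, limited to medication that could spoil the profile (11.2) or is *excluded* (SAP 10.1). Exclusion criterion 9 exempts hormonal contraceptives.
- *Loss of one period.* 11.2 and SAP 10.2 both need valid endpoints in both periods, so excluding one period removes the subject from the ANOVA.

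SAP 10.1 cannot be an automatic exclusion list. It also names out-of-window sampling, which SAP 8 keeps by using actual times. Some judgement is therefore intended.

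**2. The plan's own figure**

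Protocol 11.3 claims at least 90% power with 44 evaluable subjects at ratios 0.95 to 1.05. The CV is redacted, so I solved for it. With N as the total and the distance taken to the nearer limit, the plan's formula at ratio 0.95 gives

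s² = 44 × (0.2231 − 0.0513)² / [2 × (1.2816 + 1.6449)²] = 0.0759, so CV = √(exp(0.0759) − 1) = 28.1%.

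Exact two one-sided tests power (22 per sequence, 42 degrees of freedom) gives a ceiling of 27.5% at ratio 0.95 and 27.9% at 1.05. The claim is consistent with any CV up to about 27.5%.

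**3. Shift in the ratio**

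The log treatment difference is the average of two sequence means. With 22 per sequence, k net test-period events with relative exposure d multiply the ratio by exp[(k/44) × ln d].

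| k | d = 0.7 | d = 0.5 |
|---|---|---|
| 1 | −0.81% | −1.56% |
| 2 | −1.61% | −3.10% |

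**4. How often the verdict changes**

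Simulation per endpoint, 40,000 runs per cell: 90% interval from the ANOVA with events kept (n = 44) against dropped (n = 44 − k).

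| True ratio | CV | k=1, d=0.7 | k=1, d=0.5 | k=2, d=0.7 | k=2, d=0.5 |
|---|---|---|---|---|---|
| 0.95 | 20% | 0.7% | 2.0% | 1.6% | 6.7% |
| 0.95 | 25% | 2.4% | 5.3% | 4.9% | 13.3% |
| 0.95 | 27.5% | 3.3% | 6.7% | 6.2% | 15.2% |
| 1.00 | 20% | 0.0% | 0.1% | 0.1% | 0.4% |
| 1.00 | 27.5% | 1.5% | 2.6% | 2.8% | 6.2% |

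At ratio 1.05 the four cells span 0.4% to 1.0% (CV 20%) and 2.8% to 7.2% (CV 27.5%). At 0.95 nearly all changes are a truly equivalent product failing because the event was kept.

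**5. Cost of exclusion**

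At CV 27.5% and ratio 0.95, power is 90.1% with 44 subjects, 89.4% with 43 and 88.7% with 42. In the extreme contraceptive case, 0.20 × 48 = 9.6, so at least 10 women. Dropping 10 leaves 38, with power of 90.9% (CV 25%) or 85.6% (CV 27.5%), still above the 80% minimum cited in 11.3.

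**The case for a change.** The best case for a change is that exclusion before bioanalysis prevents selection on concentrations but not on treatment. The clinic is open-label, no decision-maker is named, nobody is required to be unaware of the product, and the SAP does not repeat the timing rule. In the worst cell of the table the choice changes the verdict in 15.2% of trials, and the remedy would be a few words.

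Part of this stands. *Important* and *relevant* are not formally linked, because SAP 12.2.2 is a reporting rule. The documents do not rule out a decision-maker who knows the treatment. The clinical wording on vomiting (5.3.3 no. 5 against 11.2) and on medication (5.3.2 and 5.3.3 no. 8 against inclusion 10 and exclusion 9) does not match. The sponsor must reconcile it, and I take no position on how.

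The rest carries less weight. SAP 9 adopts the protocol's methods unchanged, so the timing rule holds. Before bioanalysis nobody knows on which side of 1 the estimated ratio will fall, so even someone who knows the product cannot tell which choice would help. The 15.2% needs two net events, both on test, each halving exposure, at the CV ceiling and at the edge of the planned ratios. No figure in the documents supports that pattern for two tablets of the same brand and strength. Mandatory exclusion for any concomitant medication would also remove subjects for trivial use; allowing exceptions would restore the judgement it was meant to remove.

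**Conclusion.** No change is needed. The permissive wording is real, but the plan as a whole sets the diarrhoea threshold, removes withdrawn subjects, fixes exclusions before bioanalysis, blinds the laboratory and reports every exclusion reason. Analysts following it would exclude above-threshold diarrhoea and vomiting, would judge medication by its likely effect on the profile, and would not drop women for permitted contraception. The remaining discretion over medication is a fair trade-off.

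The effect is usually small: a shift of 0.8% to 1.6% in the ratio for one net test event, and a changed verdict per endpoint in at most 6.7% of trials for one event in the cells shown. These sizes assume 30% to 50% lower exposure, events on the test product only, 44 evaluable subjects and a CV of 20% to 27.5%. The event rates are not given and the CV is redacted. No figure stated in the plan was found to be wrong.

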11.3 Sample Size Justification

The number of subjects needed for a bioequivalence study was calculated with the following equation:

$$N = \frac{2 \cdot s_w^2 \cdot (Z_{1-\beta} + Z_{1-\alpha})^2}{(\ln(\mu_T / \mu_R) - \ln(1.25))^2}$$

$$s_w^2 = \ln(1 + (CV)^2)$$

α : significance level (5%)

β : power (20%)

μ_T : average score of bioavailability parameters for the test drug

μ_R : average score of bioavailability parameters for the comparator (reference) drug

CV : intra-subject CV

CCI

CCI If these CVs are applied together with applicable bioequivalence criteria for AUC and C_{max} (0.80-1.25), and the true treatment ratio Test/Reference is allowed to vary within 0.95 and 1.05, then 44 evaluable subjects will provide at least 90% power to show bioequivalence. Per *Indonesian guidelines, Pedoman Uji Bioekivalensi, Badan Pengawas Obat dan Makanan (BPOM), Jakarta, 2015, page 20*, only 80% power is required at the minimum.

For a compensation of possible drop-outs during the study, an additional four (4) subjects shall be included based on the site's standard practice. Subjects will not be replaced, even if there are more than four (4) drop-outs.

A total of forty-eight (48) healthy adult male and female subjects shall thus be included in this study with no reserve subjects. 48 subjects will be administered with the study drug and the blood will be taken at various time points of blood sampling procedures. The blood samples from 48 subjects will be analyzed for plasma concentrations of metformin. To achieve the targeted number of eligible subjects, the number of potential subjects screened will be around two times of the sample size.

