# 7 Sample Size/Randomization

The number of subjects needed for a bioequivalence study was calculated with the following equation:

$$N = \frac{2 \cdot s_w^2 \cdot (Z_{1-\beta} + Z_{1-\alpha})^2}{(Ln(\mu_T / \mu_R) - Ln(1.25))^2}$$
$$S_w^2 = Ln(1 + (CV)^2)$$

 $\alpha$ : significance level (5%)

 $\beta$ : power (20%)

 $\mu_T$  : average score of bioavailability parameters for the test drug

 $\mu_R$  : average score of bioavailability parameters for the comparator drug

CV : intra-subject CV

CCI

. If these CVs are applied together with applicable bioequivalence criteria for AUC and Cmax (0.80-1.25), and the true treatment ratio Test/Reference is allowed to vary within 0.95 and 1.05, then 44 evaluable subjects will provide at least 90% power to show bioequivalence. Per *Indonesian guidelines*, *Pedoman Uji Bioekivalensi*, *Badan Pengawas Obat dan Makanan (BPOM)*, *Jakarta*, 2015, page 20, only 80% power is required at the minimum.

For a compensation of possible drop-outs during the study, an additional four (4) subjects shall be included based on the site's standard practice. Subjects will not be replaced, even if there are more than four (4) drop-outs.

A total of forty-eight (48) healthy adult male and female subjects shall thus be included in this study with no reserve subjects. 48 subjects will be administered with the study drug and the blood will be taken at various time points of blood sampling procedures. The blood samples from 48 subjects will be analyzed for plasma concentrations of metformin.

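### Does the printed sample-size equation, with beta at 20% and only the upper limit, undermine the stated 90% power of 44 evaluable subjects?

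*Protocol*

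**What the plan says.** Protocol 11.3 gives an equation for N. SAP 7 repeats it and introduces it with "The number of subjects needed for a bioequivalence study was calculated with the following equation". The inputs are alpha at 5%, beta at 20% (glossed as power), the intra-subject CV, and a denominator equal to the squared distance from ln(muT/muR) to ln(1.25).

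The planning CVs and some adjoining text are redacted. The visible text then applies those CVs with limits of 0.80 to 1.25, assumes that "the true treatment ratio Test/Reference is allowed to vary within 0.95 and 1.05", and concludes that "then 44 evaluable subjects will provide at least 90% power to show bioequivalence". It adds that under the Indonesian guideline "only 80% power is required at the minimum". Four subjects are added for drop-outs, giving 48.

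The decision rule is in Protocol 11.2: "Bioequivalence is concluded if the 90% confidence interval of the Test/Reference geometric means ratio is in the range of 80.00-125.00" percent, for AUC0-t and Cmax.

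**The concern.** Three features look wrong whatever the redacted CVs are.

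- **Beta.** A type II error of 20% corresponds to 80% power, yet the text claims at least 90%. Calling beta the power adds to the confusion.
- **One limit.** The denominator always measures the distance to the upper limit. For a true ratio of 0.95 the limit that matters is 0.80. Entering 0.95 in the equation as printed would give far too small an N.
- **Two endpoints.** Bioequivalence needs both AUC0-t and Cmax to pass, and the power sentence does not say whether 90% is per endpoint or joint.

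If 44 had come straight from this equation, power could be below the claimed 90%, and possibly below the 80% minimum that the text cites. The sponsor and the regulator would then be relying on an overstated chance of success.

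**Working it through.** **Inputs.** From Protocol 11.3: alpha 5%, beta 20%, 44 evaluable subjects, true ratio 0.95 to 1.05, limits 0.80 to 1.25. The design is a two-period crossover with 1:1 allocation to sequence (SAP 7). The CV is not available, so the CVs below are assumptions. The plan's 44 and 90% therefore cannot be reproduced directly.

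**1. Effect of beta.** N is proportional to (z(1-beta) + z(0.95))².
- 80% power: (0.8416 + 1.6449)² = 6.183
- 90% power: (1.2816 + 1.6449)² = 8.564
- Ratio: 8.564 / 6.183 = 1.385

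An N sized for 90% is 1.385 times an N sized for 80%, so the mismatch in the legend is real.

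**2. Effect of the single limit.** Log distances:
- ratio 1.05 to 1.25: 0.1744
- ratio 0.95 to 1.25: 0.2744 (what the equation uses)
- ratio 0.95 to 0.80: 0.1719 (what matters)

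Entering 0.95 as printed gives (0.1719 / 0.2744)² = 0.392 of the required N. Entering 1.05 gives almost the right answer for both ends. At CV 25%, s² = ln(1 + 0.25²) = 0.0606, and at 90% power:
- ratio 1.05 against 1.25: 2 × 0.0606 × 8.564 / 0.1744² = 34.2
- ratio 0.95 against 0.80: 2 × 0.0606 × 8.564 / 0.1719² = 35.2
- ratio 0.95 against 1.25, as printed: 13.8

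The documents do not say which ratio was entered.

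**3. Is 90% reachable with 44 subjects?** Exact power of the two one-sided tests, with standard error s × √(2/44), 42 degrees of freedom, and numerical integration over the variance estimate:

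| Assumed CV | Power at 0.95 | Power at 1.05 |
|---|---|---|
| 20% | 99.1% | 99.2% |
| 25% | 94.2% | 94.7% |
| 27% | 91.0% | 91.6% |
| 28% | 89.1% | 89.9% |
| 30% | 85.1% | 85.9% |
| 35% | 73.5% | 74.4% |

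The ratio 0.95 is the binding case. There, power is at least 90% for any CV up to 27.5% and at least 80% for any CV up to 32.3%. A simulation at CV 25% and ratio 0.95 also gave 94.2%.

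**4. Could the equation and the power sentence be two separate steps?** At CV 27.5%, s² = ln(1 + 0.275²) = 0.0729. The printed equation with beta 20% and ratio 1.05 gives 2 × 0.0729 × 6.183 / 0.1744² = 29.7, about 30 subjects for the 80% minimum. Forty-four subjects at the same CV give 90.1% power at ratio 0.95. An equation that yields a minimum, followed by a larger chosen N with its power stated, fits these numbers.

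**5. Joint power.** If the endpoints were independent, joint power would be the product of the two single powers. With both CVs at 27.5%: 0.901 × 0.901 = 81%. With 27.5% and 20%: 0.901 × 0.991 = 89%. With both at 25%: 0.942 × 0.942 = 89%. Positive correlation raises these; with both CVs at 27.5% and correlation 0.8, simulation gives 86%.

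**The case for a change.** The strongest case for a change is that the text says N was calculated with the equation, and that the equation cannot by itself yield a true 90%. Setting N = 44, solving for the CV and then computing exact power at ratio 0.95 gives:

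- beta 20%, ratio 1.05: CV 33.8%, power about 76%
- beta 10%, ratio 1.05: CV 28.5%, power 88.2%
- beta 10%, ratio 0.95 as printed: CV 46.2%, power 45%

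On this argument, either the claim misses or the equation is not the source of 44, and in both cases the text should be corrected.

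Part of this stands. Beta is mislabelled, its value does not belong to a 90% claim, the denominator is wrong for ratios below 1, and the visible text names no method for the 90%. The low-power figures do not stand as findings. They rest on CVs that appear nowhere in the documents and were obtained by assuming that 44 is the equation's output. The 45% case also supposes that 0.95 was entered against the upper limit, for which there is no evidence. The power sentence brings in both limits and a range of ratios, neither of which the equation can take, and this points to a separate calculation.

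The joint-power point is a preference. The documents claim no joint power, and the size of any shortfall depends on the redacted CVs.

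**Conclusion.** No change to the plan is called for. The discrepancy in the legend and formula is real but clerical, and the missing method is a gap in documentation. The stated 90% is not shown to be wrong: per endpoint, with 44 evaluable subjects, it holds across ratios 0.95 to 1.05 if the larger intra-subject CV is at most about 27.5%, and the 80% minimum holds up to about 32.3%. Whether the planning CVs lie within those bounds cannot be judged from the public text, and their redaction is not a fault of the plan.

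Tidying the equation would alter neither the 48 subjects nor the analysis. The 90% confidence interval rule controls the risk of a false claim of bioequivalence whatever power was planned. The conclusion assumes balanced sequences and the usual log-normal crossover model. It would need another look only if the unredacted CVs proved to exceed these bounds.

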12 ADVERSE EVENTS/TOXICITY

12.1 Definition of an Adverse Event

An AE is any untoward medical occurrence in a subject or clinical investigation subject administered a pharmaceutical product, regardless of causal relationship with this treatment. An AE can therefore be any unfavorable and unintended sign (including an abnormal laboratory finding), symptom, or disease temporally associated with the use of a medicinal product, whether or not considered related to the medicinal product.

For surgical or diagnostic procedures, the condition/illness leading to such a procedure is considered as the AE rather than the procedure itself.

Subjects will be instructed by the Investigator/study physician to report the occurrence of any adverse event. The Investigator is required to grade the severity or toxicity of each AE.

Investigators must assess the severity of AEs according to the Qualitative Toxicity Scale, as follows:

- | | |
|-----------|---|
| Mild: | The subject is aware of the event or symptom, but the event or symptom is easily tolerated. |
| Moderate: | The subject experiences sufficient discomfort to interfere with or reduce his or her usual level of activity. |
| Severe: | Significant impairment of functioning: the subject is unable to carry out his or her usual activities. |

Investigators must also systematically assess the causal relationship of AEs to the study drugs (including any other non-study drugs, study procedures, etc.) using the following definitions. Decisive factors for the assessment of causal relationship of an AE to metformin hydrochloride (Glucophage® XR) include, but may not be limited to, temporal relationship between the AE and metformin hydrochloride (Glucophage® XR), known side effects of metformin hydrochloride (Glucophage® XR), medical history, concomitant medication, course of the underlying disease, study procedures.

Unrelated: Not reasonably related to the study drugs. AE could not medically (pharmacologically/clinically) be attributed to the drugs under study in this study protocol. A reasonable alternative explanation must be available.

Related: Reasonably related to the study drugs. AE could medically (pharmacologically/clinically) be attributed to the drugs under study in this study protocol.

Abnormal Laboratory Findings and Other Abnormal Investigational Findings

Abnormal laboratory findings and other abnormal investigational findings (for example, on an ECG trace) should not be reported as AEs unless they are associated with clinical signs and symptoms, lead to treatment discontinuation or are considered otherwise medically important by the Investigator. If a laboratory abnormality fulfills these criteria, the identified medical condition (for example, anemia, increased ALT) must be reported as the AE rather than the abnormal value itself.

Serious Adverse Events

An SAE is any untoward medical occurrence that at any dose:

- Results in death.
- Is life-threatening. (Note: The term "life-threatening" refers to an event in which the subject is at risk of death at the time of the event, not an event that hypothetically might have caused death if it was more severe.)
- Requires inpatient hospitalization or prolongs an existing hospitalization.
- Results in persistent or significant disability or incapacity.
- Is a congenital anomaly or birth defect.
- Is otherwise considered to be medically important. (Note: Important medical events that may not result in death, be life-threatening, or require hospitalization may be considered as SAEs when, based upon appropriate medical judgment, they may jeopardize the subject or may require medical or surgical intervention to prevent one of the outcomes listed above. Examples of such events include allergic bronchospasm requiring intensive treatment in an emergency room or at home, blood dyscrasias or convulsions that do not result in inpatient hospitalization, or the development of drug dependency or drug abuse.)

For the purposes of reporting, any suspected transmission of an infectious agent via a study drug is also considered an SAE, as described in Section 12.1.

Events that Do Not Meet the Definition of an SAE

Elective hospitalizations to administer, or to simplify study procedures (for example, an overnight stay to facilitate pre-drug administration procedures) are not considered SAEs. However, all events leading to unplanned hospitalizations or unplanned prolongation of an

elective hospitalization (for example, undesirable effects of any administered study drugs and/or procedures) must be documented and reported as SAEs.

Events Not to Be Considered as AEs/SAEs

Medical conditions present at the Screening visit that do not worsen in severity or frequency during the study are defined as Baseline Medical Conditions, and are not to be considered AEs.

Definition of the Adverse Event Reporting Period

The AE reporting period for safety surveillance begins when the subject is initially included in the study (date of first signature on the informed consent form [ICF]) and continues until the last post-treatment safety visit, which in this case is completion of the Follow-Up Visit.

Any SAE assessed as related to metformin hydrochloride (Glucophage® XR) must be reported whenever occurs, irrespective of the time elapsed since the last administration of metformin hydrochloride (Glucophage® XR).

Procedure for Reporting Serious Adverse Events

In the event of any new SAE occurring during the reporting period, the Investigator must immediately (within a maximum of 24 hours after becoming aware of the event) inform the Sponsor in writing. All written reports should be transmitted using Merck SAE Report Form, which must be completed by the Investigator following specific completion instructions.

In exceptional circumstances, an SAE (or follow-up information) may be reported by telephone; in these cases, a written report must be sent immediately thereafter by e-mail to [contact].

Relevant pages from the CRF may be provided in parallel (for example, medical history, concomitant drugs). Additional documents may be provided by the Investigator, if available (for example, laboratory results, hospital report, autopsy report). In all cases, the information provided on the SAE Report Form must be consistent with the data about the event recorded in the CRF.

The Investigator must respond to any request for follow-up information (for example, additional information, outcome, final evaluation, other records where needed) or to any question the Sponsor may have on the AE within the same timelines as those noted above for initial reports. This is necessary to ensure prompt assessment of the event by the Sponsor to allow the Sponsor to meet strict regulatory timelines associated with expedited safety and tolerability endpoints reporting obligations.

Merck Global Drug Safety department may contact the Investigator to obtain further information or to discuss the event.

Safety Reporting to Local Health Authority, Ethics Committee and Investigator

The Sponsor will send appropriate safety notifications to the local Health Authority, *Badan Pengawas Obat dan Makanan* (BPOM) in accordance with applicable laws and regulations.

The Investigator must comply with any applicable site-specific requirements related to the reporting of SAEs (particularly deaths) involving trial subjects to the Ethics Committee that approved the study.

In accordance with ICH GCP, the Sponsor will inform the Investigator of "findings that could adversely affect the safety of subjects, impact the conduct of the trial or alter the IEC's/IRB's approval/favorable opinion to continue the trial." In particular and in line with respective regulations, the Sponsor will inform the Investigator of AEs that are both serious

and unexpected and are considered to be related to the administered drugs ("suspected unexpected serious adverse reactions" or SUSARs). The Investigator should place copies of Safety Reports in the Investigator Site File. BPOM regulations with regard to Safety Report notifications to Investigators will be taken into account.

The Investigator will be responsible for promptly notifying the concerned Ethics Committee of any Safety Reports provided by the Sponsor and of filing copies of all related correspondence in the Investigator Site File.

Monitoring of Subjects with Adverse Events

AEs are recorded and assessed continuously throughout the study and are assessed for final outcome at the Follow-up Visit. All SAEs ongoing at the Follow-up Visit must be monitored and followed up by the Investigator until stabilization or until the outcome is known, unless the subject is documented as "lost to follow-up". Reasonable attempts to obtain this information must be made and documented. It is also the responsibility of the Investigator to ensure that any necessary additional therapeutic measures and follow-up procedures are performed.

